COVER PAGE

STATISTICAL ANALYSIS PLAN

**OFFICIAL TITLE: Investigation of The Effect of Training Given According to Roy
Adaptation Model On Adaptation to The Disease in Patients With Hypertension A
Single-Blind Randomized Controlled Study With Pretest-Posttest**

DATE OF DOCUMENT: July 20, 2018

Statistical Analysis Plan

As a result of the power analysis performed using Gpower version 3.1.9.2; while Type 1 error amount (alpha) was 0.05, test power (1-beta) was 0.8, effect size was 0.91 and alternative hypothesis (H1) was two-sided, the minimum sample size required to obtain a significant difference by using this test was determined as 21 subjects in each group. However, considering that there might be losses in the study, the sample of the study was composed of a total of 68 patients including 34 in the experimental group and 34 in the control group who applied to the cardiology clinic and outpatient clinic of a university hospital, met the inclusion criteria and were diagnosed with hypertension. The study was completed with a total of 60 patients including 30 in the experimental group and 30 in the control group because of the communication problem with two (2) patients from the experimental group and the death of two (2) patients from the experimental group and the communication problem with four (4) patients from the control group during the study.

Randomization was performed by a statistician who had no contact with the participants and randomized them to the experimental and control groups by generating random numbers from MedCalc 18.2.1 software. The participants were randomly divided into intervention and control groups including 34 participants in each. However, four patients from the experimental group and four patients from the control group were excluded from the study while the study was continuing. The patients were informed about the study and their informed consents were obtained. In this study, the participants of the experimental and control groups were blinded to each other; however, the researcher was not blind to the group assignment due to the nature of the study. The participants in the experimental group were invited to be a part of a hypertension training program. This study lasted for approximately 5 months. The training program was given in an appropriate room in the cardiology outpatient clinic of a university hospital and the interaction between the two groups was inhibited.

Figure 1 shows the flow chart of the study.

The statistical evaluation of the data obtained as a result of the study was performed by using 24.0 version of SPSS program and $p < 0.05$ was accepted as statistically significant. In order to control if the continuous variables are suitable for normal distribution, Shapiro Wilk test was used. For the statistical analysis of the data obtained as a result of the study, mean \pm standard deviation, percentage, Chi-square test, Mann Whitney U test, Wilcoxon test and Cronbach's alpha internal consistency test were used.

Figure 1. Flow diagram of the study.

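### Does the blinding described in the SAP contradict the single-blind label in its title?

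*SAP*

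**What the plan says.** The cover page gives the design as a "Single-Blind Randomized Controlled Study With Pretest-Posttest". Blinding is then described once, in the randomization paragraph: "the participants of the experimental and control groups were blinded to each other; however, the researcher was not blind to the group assignment", which the SAP attributes to the kind of study it is.

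The same paragraph bears on the point in four further places:

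- Allocation: "Randomization was performed by a statistician who had no contact with the participants", using software-generated random numbers.
- Arm sizes: "The participants were randomly divided into intervention and control groups including 34 participants in each".
- What the trained arm was told: "The participants in the experimental group were invited to be a part of a hypertension training program". It also says that patients were informed about the study and consented, without saying what they were told about the two arms.
- Separation of the arms: "the interaction between the two groups was inhibited".

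The closing paragraph on statistical evaluation lists the tests and ends with Cronbach's "alpha internal consistency test were used". It does not mention masked outcome assessment or masked analysis.

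**The concern.** Single-blind is usually read as meaning that one identifiable party did not know which intervention a patient received. Going through the parties in the SAP, it is hard to find one. The researcher is said not to be blind. Patients in the training arm were asked to attend sessions and must have known it. The statistician had no contact with participants but produced the allocation. Being blinded to each other, taken together with the separation of the groups, could describe no more than a measure against contamination.

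If so, the title would suggest a protection that the trial did not have. The title makes adaptation to the disease the outcome, and the internal-consistency check suggests a multi-item scale. If patients complete such a scale themselves, knowing that they were trained can shift their answers. If the unblinded researcher administers it, assessment can be biased as well. A reader who takes the label at face value would give the result too much credit.

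**Working it through.** **1. Does any figure in the plan depend on blinding?** The only design figure is 21 per group, from two-sided alpha 0.05, power 0.80 and effect size 0.91.

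- Normal approximation: n = 2(1.960 + 0.842)² / 0.91² = 2 × 7.85 / 0.8281 = 18.96, so 19 per group.
- Exact two-sample t-test: noncentrality 0.91 × √(20/2) = 2.88 on 38 degrees of freedom gives power 0.801, so 20 per group.
- Mann-Whitney test with asymptotic relative efficiency 3/π = 0.955: 21 per group counts as 21 × 0.955 = 20.05, noncentrality 0.91 × √(20.05/2) = 2.88, power 0.802. With 20 per group the power is 0.781, so 21 are needed.

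The stated 21 is reproduced under the Mann-Whitney test, which the SAP lists. Blinding enters none of these formulas, so rewording the label cannot move the number.

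**2. What each party is said to know.**

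| Party | What the SAP says | What follows |
|---|---|---|
| Researcher | Not blind to group assignment | Unmasked, and disclosed |
| Training arm (34) | Asked to attend a training programme | Knew what they received (inferred, but close to certain); may not have known of another arm |
| Control arm (34) | Covered by "the participants of the experimental and control groups were blinded to each other" | May or may not have been unaware of the training; not stated |
| Statistician | Generated the allocation, no contact with participants | Bears on sequence generation, not on masked analysis |
| Outcome assessor | Not mentioned | Cannot be judged from the SAP alone |

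**3. How many patients could have been unaware of the training?** Randomised: 68 − 34 = 34, or 34/68 = 50%. Completers: 60 − 30 = 30, or 30/60 = 50%. These are ceilings. They restate the size of the control arm and do not estimate bias.

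**4. Contradiction or ambiguity?** In the blinding sentence, participants are the ones blinded, and the word *however* sets them against the unblinded researcher. One side blinded and the other not is the ordinary form of a single-blind statement, and it agrees with the title. Separation of the groups is stated a few sentences later as a point of its own, so the blinding sentence need not be a second way of saying the same thing. It can also mean that each arm did not know of the other, or did not know what the other received. The text supports both readings and settles neither. What is missing is the object of the blinding: unaware of what?

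**The case for a change.** The strongest case for acting is that the document supplies both the label and the description, so the mismatch cannot be passed to a protocol that is not at hand. On the reading most favourable to the authors, each arm was unaware of the other. Even then the 34 trained patients knew their own intervention, so half the trial was unmasked in the sense most readers would assume. Correcting the wording costs a sentence or two.

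Part of this stands. The sentence is loose, and it does not establish that participants were unaware of their own intervention. A reader should not credit the trial with conventional participant masking on the strength of the title.

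The rest does not carry. Replacing the label with a statement that participants were not masked would go beyond the document, which is silent on what control patients knew. It could exchange an unclear statement for a false one. The bias argument rests on things the SAP does not state: the instrument, whether patients complete it themselves, and who collects it. These are commonly left to a protocol. A sentence on limitations belongs in the study report. Analysis on coded groups would have been a real safeguard against analyst bias, though not against response bias, but the SAP describes the statistical evaluation in the past tense as already performed.

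**Conclusion.** No change to the plan follows. Title and text agree in the authors' evident sense: participants on the blinded side, researcher not. What participants were blinded to is left unsaid, which is a lack of detail and not a conflict. Filling it in would change no sample size, test, dataset or estimate, and the size of any resulting bias cannot be derived from the document. The most that can be said is that no more than 34 of 68 randomised patients, or 30 of 60 completers, could have been unaware of the training.

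This rests on two assumptions: that patients asked to attend training knew they were trained, and that the word *however* contrasts blinded participants with an unblinded researcher. Knowledge of one's own arm is hard to avoid in an education trial, and the SAP is open about the researcher. Anyone interpreting the result can therefore treat the trained arm and the researcher as unmasked, and take the label to mean at most that the arms were unaware of each other.

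### Must the plan name a between-arm effect estimate and confidence interval beside its rank tests?

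*SAP*

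**What the plan says.** The SAP has two relevant parts, both under the heading Statistical Analysis Plan.

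- **Statistical evaluation paragraph.** A p-value below 0.05 "was accepted as statistically significant". Shapiro-Wilk is used to check normality. The methods are mean with "standard deviation, percentage, Chi-square test, Mann Whitney U test, Wilcoxon test and" Cronbach's alpha. No difference between arms, standardised or otherwise, is named as something to be estimated, and no confidence interval is mentioned.
- **Sample size paragraph.** "Type 1 error amount (alpha) was 0.05", "test power (1-beta) was 0.8", a two-sided alternative and "effect size was 0.91" are the inputs, and the minimum "by using this test was determined as 21 subjects in each group". The 0.91 is a planning input, not a planned estimate. The study was "completed with a total of 60 patients including 30 in the experimental group and 30 in the control group".

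The title calls the trial a "Single-Blind Randomized Controlled Study With Pretest-Posttest". Neither part says whether the comparison between arms, or the 0.91, refers to posttest or change scores.

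**The concern.** How the arms are compared and summarised is core SAP content, so a missing protocol does not explain the silence. As listed, the Mann-Whitney and Wilcoxon tests deliver p-values only. In a trial of 60 completers a p-value leaves the size of the effect wide open in both directions. A non-significant result can sit with an interval that still contains the planning value of 0.91 SD, and a significant one can have a lower limit close to zero. If p < 0.05 were the only thing reported, readers could take a failed test as evidence of no effect, or a passed one as evidence of a worthwhile effect. Means and SDs by arm do not obviously close the gap, because the plan does not commit to a difference between them and a mean difference is not the quantity a rank test addresses.

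**Working it through.** **Inputs.** From the sample size paragraph: two-sided alpha 0.05, power 0.8, effect size 0.91, 21 per group required, 30 per group completed. From the statistical evaluation paragraph: rank tests, mean with SD, p < 0.05. Assumed, because the SAP gives no outcome SD: 0.91 is a standardised mean difference, scores are roughly normal and untied, and the arms differ by a pure shift.

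**1. The plan's own figure.** A two-sample t-test with d = 0.91 has power 0.801 at 20 per group. For a Mann-Whitney test with normal scores, multiply n by the relative efficiency 3/π = 0.955:

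- n = 20: effective 19.1 per group, power 0.781
- n = 21: effective 20.05 per group, noncentrality 0.91 × √(20.05/2) = 2.88, power 0.802

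The stated 21 is therefore reproduced by a Mann-Whitney calculation. That is an inference, since the paragraph does not name the test. The sample size is not in dispute.

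**2. What 30 per arm can show.** The same formula with n = 30 gives:

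| True difference (SD) | Power |
|---|---|
| 0.3 | 0.200 |
| 0.5 | 0.460 |
| 0.75 | 0.796 |
| 0.91 | 0.923 |

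**3. Width of the interval that is not named.** On the rank-test scale, SE = √(2/30) × √(π/3) = 0.258 × 1.023 = 0.264 SD. In simulated trials, the 95% Hodges-Lehmann interval (from inverting the exact Mann-Whitney test) averages 1.06 SD wide.

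An interval excludes 0.91 SD only if the estimate is below 0.91 − 1.96 × 0.264 = 0.392 SD. That is z = 0.392/0.264 = 1.48, or p of about 0.14. So a result favouring training with p between 0.05 and about 0.14 does not exclude the planning value. Over all non-significant trials with a true difference of 0.5 SD, about 60% of intervals exclude 0.91 SD and about 5% exclude 0.5 SD. Among significant trials at that same true difference, the median lower limit is 0.17 SD. The p-value alone does not separate these cases.

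**4. What the listed summaries already give.** With mean and SD by arm and 30 patients in each, the interval for the mean difference is

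difference ± t(0.975, 58 df) × SD × √(2/30) = difference ± 2.002 × 0.258 SD = difference ± 0.517 SD,

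which is about 1.03 SD wide. Compared with the Hodges-Lehmann interval in the same simulated trials (true difference 0, 0.5 or 0.91 SD):

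- mean width 1.03 against 1.06 SD
- lower limits differ by 0.05 SD on average (correlation 0.98)
- the two agree on whether 0.5 or 0.91 SD is excluded in 93% to 98% of trials

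**5. What an added interval would change.** The tests, p-values, sample size and precision all stay the same. The interval makes the existing information visible; it does not create any.

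**The case for a change.** The strongest case for a change is that the plan commits to nothing beyond p-values and arm-wise description. It does not say that mean and SD will be tabulated by arm and time point. A reader who forms an interval from them gets one for the mean difference, not for the shift that a Mann-Whitney test addresses. The agreement in step 4 is also computed under normality, whereas the plan screens for normality and lists only rank tests for continuous scores; with skewed or heavily tied scores the two intervals could part company. For change scores, the pretest and posttest SDs are not enough; the SD of the change is needed too. And the remedy is cheap: one sentence and a little output from data already held.

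All of that stands as an argument for better reporting. It does not show that the plan is wrong. Nothing in the SAP says that p-values will be reported alone or that a non-significant p will be read as no effect; the harm is a misreading that the document does not invite. The normality assumption also cuts both ways, because the interval widths and exclusion rates used to press the concern rest on it as well. They would describe any two-arm study with 30 per arm. Whether the contrast uses posttest or change scores is a separate ambiguity about what is tested, and it lends no weight to a request for an interval.

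**Conclusion.** No change to the plan is needed. The SAP does omit a between-arm estimate and interval, and at 30 per arm that interval would be wide, about 1.06 SD. But the listed tests are valid, no statement in the SAP is false on this point, and following it as written gives sound p-values. If posttest means and SDs are shown by arm, an interval of about 1.03 SD can be formed from them that leads to the same reading in 93% to 98% of simulated trials.

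This rests on roughly normal, untied scores, a pure shift between arms, 0.91 being a standardised mean difference, and summaries being reported by arm. If those fail, the recoverable interval is a poorer guide, but the planned tests remain valid.

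Reporting a Hodges-Lehmann difference with its 95% interval beside each Mann-Whitney p-value would be good practice. It would be post hoc, because the document already describes a completed study, and reading it as a shift needs similar distribution shapes in the two arms. It is a reporting preference that a sensible analyst can meet without an amended plan.

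### A pretest is collected, but no listed test compares the arms on the posttest adjusted for it; the unadjusted Mann-Whitney test is valid but gives up power

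*SAP*

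**What the plan says.** The official title on the SAP's cover page calls the trial a "Single-Blind Randomized Controlled Study With Pretest-Posttest", so a baseline score is part of the design.

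The power paragraph states that "effect size was 0.91" with two-sided alpha 0.05 and power 0.8, and arrives at 21 per group. It then reports: "The study was completed with a total of 60 patients including 30 in the experimental group and 30 in the control group".

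The statistical evaluation paragraph at the end of the SAP lists the methods. It says that to check "if the continuous variables are suitable for normal distribution, Shapiro Wilk test was used", and for the analysis it names means with standard deviations, then "percentage, Chi-square test, Mann Whitney U test, Wilcoxon test and" Cronbach's alpha. For scores, that leaves Mann-Whitney between arms and, by inference, Wilcoxon for the paired comparison within an arm. The SAP does not say whether Mann-Whitney is applied to the posttest or to the change from pretest.

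**The concern.** In a randomised trial with a baseline measurement of the outcome, the natural between-arm analysis takes the posttest and adjusts for the pretest. Nothing on the SAP's list does this. Mann-Whitney on the posttest discards the pretest. Mann-Whitney on the change uses it, but in effect fixes its slope at 1, which adds noise when the pre/post correlation is low.

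Two things are at stake. The first is power: 30 patients per arm is a small trial, and the pretest can sharpen the comparison without further patients. The second is interpretation: with 30 per arm the pretest means will often differ by chance, and an unadjusted posttest difference then partly reflects that starting difference.

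This point alleges neither bias nor a sample-size error. Nor does it claim that the plan would judge efficacy from within-arm Wilcoxon results, since the SAP does not say so.

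**Working it through.** **Inputs from the SAP.** Two-sided alpha 0.05, power 0.80, effect size d = 0.91, 21 per group required, 30 per group completed. **Assumed, because the SAP does not give them:** pre/post correlation ρ of 0.3, 0.5 or 0.7; a moderate alternative effect of 0.5 SD; equal SDs; normal scores, with lognormal scores as a skewed variant.

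**Step 1: reproduce the plan's 21 per group.** For Mann-Whitney, use the noncentral t with effective size n′ = n × 3/π, df = 2n′ − 2 and noncentrality d√(n′/2).

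- n = 20: n′ = 19.10, noncentrality 0.91 × √9.55 = 2.81, power 0.781.
- n = 21: n′ = 20.05, noncentrality 0.91 × √10.03 = 2.88, power 0.802.

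So 21 is the first size to reach 0.80. A t-test would need 20 (power 0.801). The stated figure matches an unadjusted between-arm Mann-Whitney test, so that comparison is evidently the planned one.

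**Step 2: the same test at 30 per arm.** n′ = 28.65 and √(n′/2) = 3.785.

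- d = 0.91: noncentrality 3.44, power 0.92.
- d = 0.5: noncentrality 1.89, power 0.46.

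**Step 3: adjust for the pretest.** ANCOVA shrinks the residual SD by √(1 − ρ²), so the effect becomes d/√(1 − ρ²), with df = 2n − 3 = 57 and noncentrality equal to that effect × √15. For d = 0.5:

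- ρ = 0.3: 0.5/0.954 = 0.524, noncentrality 2.03, power 0.51.
- ρ = 0.5: 0.5/0.866 = 0.577, noncentrality 2.24, power 0.59.
- ρ = 0.7: 0.5/0.714 = 0.700, noncentrality 2.71, power 0.76.

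For a change score the effect is d/√(2(1 − ρ)). At ρ = 0.3 this is 0.5/√1.4 = 0.423, smaller than the 0.5 available without using the pretest at all.

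**Step 4: simulation, 10,000 trials per cell, 30 per arm.** Rank ANCOVA regresses the posttest ranks on arm and pretest ranks. Entries are power at ρ = 0.3 / 0.5 / 0.7.

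| Method | Normal, 0.5 SD | Normal, 0.91 SD | Skewed, 0.5 SD |
|---|---|---|---|
| Mann-Whitney, posttest | 0.453 / 0.456 / 0.448 | 0.921 / 0.918 / 0.919 | 0.643 / 0.636 / 0.637 |
| Mann-Whitney, change | 0.353 / 0.450 / 0.660 | 0.804 / 0.914 / 0.991 | not run |
| Rank ANCOVA | 0.489 / 0.559 / 0.700 | 0.935 / 0.966 / 0.996 | 0.679 / 0.746 / 0.875 |
| ANCOVA | 0.510 / 0.591 / 0.750 | 0.947 / 0.975 / 0.998 | 0.531 / 0.588 / 0.738 |

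The skewed scores are lognormal with log-SD 0.5 and ρ on the log scale. If ρ = 0 and the effect is 0.5 SD (normal), Mann-Whitney on the posttest has 0.450 and rank ANCOVA 0.453, so adjusting for a useless pretest costs essentially nothing.

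**Step 5: smallest effect with 80% power at 30 per arm (t approximation).** Mann-Whitney 0.75 SD; ANCOVA 0.70, 0.64 or 0.53 SD.

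**Step 6: no true effect.** Overall rejection is 0.044 to 0.055 for every method. The SD of the difference in pretest means is √(2/30) = 0.258 SD, so a difference above 0.3 SD in either direction has probability 2 × [1 − Φ(0.3/0.258)] = 0.245, about a quarter of trials. Within those trials (normal scores), Mann-Whitney on the posttest rejects in 0.063 / 0.102 / 0.147, against 0.039 / 0.050 / 0.051 for rank ANCOVA.

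**The case against.** The strongest reply is that nothing here is an error. Mann-Whitney is valid, holds its level, and matches the stated sample size. On the plan's own figures the trial has about 92% power, above its 80% target, and rank ANCOVA adds only about 1 to 8 percentage points. The large contrasts need a smaller effect and a substantial correlation, neither of which is in the SAP. All of that stands, and it limits the point to efficiency. But 92% holds only if the true effect is 0.91 SD, and unadjusted power falls below 80% for effects under about 0.75 SD.

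Second, Mann-Whitney may be meant for the change score, which does use the pretest. At ρ = 0.7 and 0.5 SD the gap is then only 0.66 against 0.70. That is fair, but at ρ = 0.3 it is 0.35 against 0.49. Rank ANCOVA was ahead of both versions in every simulated cell where they were compared.

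Third, the 6%, 10% and 15% rejection rates describe a selected quarter of null trials and are not an inflated type I error. That is correct. With overall rejection near 5%, the rate in the other trials must be lower; at ρ = 0.5 it is about (0.05 − 0.25 × 0.102)/0.75 = 0.033. The figures show what adjustment does for a trial that happens to be imbalanced, and nothing more.

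Fourth, the SAP is in the past tense with completed counts, so a change may come too late to replace the primary result. That also stands and is reflected in the fix.

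**Conclusion.** The concern holds as a loss of efficiency. The SAP collects a pretest and lists no between-arm comparison of the posttest adjusted for it. With 30 per arm and normal scores, the power given up against rank ANCOVA is about 4, 10 or 25 points at a 0.5 SD effect for ρ = 0.3, 0.5 or 0.7, and about 1, 5 or 8 points at the planned 0.91. With ρ near zero there is no loss. These sizes rest on the assumed correlation, effect and score distribution, since the SAP gives only the 0.91.

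Plain ANCOVA does slightly better with normal scores, but with skewed scores it falls below the unadjusted Mann-Whitney test at ρ = 0.3 and 0.5. Rank ANCOVA is therefore the safer single choice. The change should be made, but the trial's validity does not depend on it.

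**What to change.** State in the statistical evaluation paragraph that the efficacy conclusion rests on one between-arm comparison of the posttest adjusted for the pretest, at two-sided 0.05. Use a single method fixed in advance and not chosen by the Shapiro-Wilk result. Rank ANCOVA (posttest ranks on arm and pretest ranks) fits the plan's rank-based approach. Say that within-arm Wilcoxon results are descriptive.

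If the data have already been analysed, as the SAP's past tense suggests, keep the Mann-Whitney result, state whether it was run on the posttest or the change, and report the adjusted analysis beside it, labelled as added later. In that case it is supportive and cannot replace the Mann-Whitney result.

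The cost is one or two sentences, with no change to sample size or data collection. The drawback is that a rank ANCOVA coefficient is harder to interpret than a difference in scores. Ordinary ANCOVA would be easier to read, but it assumes linearity and loses power with skewed scores.
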